2. OBJECTIVES

Primary Objective:

To determine the five-year incidence of histologically confirmed cervical cancer in HPV-positive women with low-grade cytological abnormalities detected through the Dutch cervical cancer screening program.

Secondary Objectives:

- To assess time to cervical cancer diagnosis, all-cause mortality, type of examination at which the diagnosis was established and the histological characteristics of the carcinoma (subtype) in this population , within five years after enrollment.
- To assess cervical cancer risk stratified by histological diagnosis within three months of baseline abnormal cytology (\leq CIN 1 vs CIN 2+) and, for the \leq CIN 1 group, further stratified by cytology at 12-month follow-up (no or nondiagnostic cytology, \leq LSIL, HSIL +), with a follow-up period of five years and three months after enrollment.
- To perform a sub-analysis of women with a history of abnormal cytology or histology and assess their five-year cervical cancer risk.
- To evaluate the incidence of cervical cancer in women with stable NILM cytology after one year and compare it to the five-year incidence in women with low-grade cytological abnormalities.

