3. STUDY DESIGN

This retrospective cohort study includes women who participated in the Dutch national cervical cancer screening program between January 2017 and December 2018, with a follow-up period of five years.

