4. STUDY POPULATION

4.1 Population (base)

The study population consists of women who participated in the Dutch national cervical cancer screening program between January 2017 and December 2018. Eligible women were HPV-positive at baseline with either low-grade cytological abnormalities (ASC-US, AGC, LSIL) or stable NILM cytology one year after initial screening.

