4.2 Inclusion criteria

To be eligible to participate in this study, a participant must meet the following criteria:

- Women participating in the Dutch national cervical cancer screening program between January 2017 and December 2018.
- HPV-positive at baseline screening.
- One of the following cytology results:
 - ASC-US, AGC, or LSIL cytology according to the Bethesda system

or

- NILM cytology at one-year follow-up.

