4.3 Exclusion criteria

There are no exclusion criteria.

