5. METHODS

5.1 Study parameters/endpoints

5.1.1 Main study parameter/endpoint

- Incidence of histologically confirmed cervical cancer within the five-year screening interval in HPV-positive women with low-grade cytological abnormalities.

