6. STATISTICAL ANALYSIS

6.1 Primary study parameter(s)

The primary study parameter is the incidence of histologically confirmed cervical cancer within the five-year follow-up period. The cumulative incidence will be calculated as the number of new cases diagnosed divided by the total number of women included in the cohort. The incidence rate will also be calculated as the number of cervical cancer cases divided by the total follow-up time in person-years and expressed per 1,000 person-years.

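### The comparison of stable-NILM with low-grade women has no stated time origin for the NILM group; on one natural reading the NILM benchmark is understated by about 20%

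*Combined protocol and SAP*

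**What the plan says.** The comparison is the fourth secondary objective in section 2: "To evaluate the incidence of cervical cancer in women with stable NILM cytology after one year and compare it to the five-year incidence" in low-grade women. The five-year label is attached to the low-grade side only. The Summary's rationale makes stable-NILM women the yardstick for judging whether follow-up of low-grade women can be made less intensive.

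Entry differs by group. Section 4.1 requires "stable NILM cytology one year after initial screening" and section 4.2 "NILM cytology at one-year follow-up" for the NILM group. Low-grade women enter on their baseline abnormal cytology. Section 4.3 adds: "There are no exclusion criteria".

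On the window, section 3 describes participation "between January 2017 and December 2018, with a follow-up period of five years" for the whole cohort. Section 5.1.1 counts cancers "within the five-year screening interval in HPV-positive women with low-grade cytological abnormalities". Other outcomes are timed from enrollment, a term that is not defined for either group. One low-grade analysis, by histology within three months, runs "with a follow-up period of five years and three months after enrollment".

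On the estimators, section 6.1 divides new cases by all women included, and defines the rate as "the number of cervical cancer cases divided by the total follow-up time in person-years" without saying when person-time starts. Section 6.2 applies both measures to the NILM group. It gives no window, landmark or measure of contrast for the comparison.

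**The concern.** A woman diagnosed with cancer during the first year would in practice not go on to have a one-year NILM cytology, so she cannot appear in the NILM group. A low-grade woman diagnosed in the same period stays in the low-grade numerator. If the NILM clock also starts at baseline, the NILM group carries a year in which no event can occur, and its incidence is diluted.

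Two analysts could follow the plan faithfully and report different benchmarks. The two planned measures, cumulative incidence and rate, could also disagree with each other purely because of the clock. Since the NILM figure gives the low-grade result its policy meaning, the origin should be fixed before the data are analysed.

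**Working it through.** The plan states no expected incidence, sample size or precision, so it has no figure to reproduce. The check isolates the effect of the clock.

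**Inputs**
- Follow-up of five years (section 3).
- NILM selection at one year (sections 4.1 and 4.2).
- Cumulative incidence = cases / women; rate = cases / person-years (sections 6.1 and 6.2).
- Assumed: the same constant annual hazard *h* in both groups and rare events, so that risk over *k* years at risk is about *kh*. A fair comparison should then return 1.00.

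Low-grade women, baseline to year five: risk 5*h*, rate 5*h*/5 = *h*.

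| NILM window | NILM risk | NILM rate | Risk ratio (low-grade/NILM) | Rate ratio |
|---|---|---|---|---|
| A. Baseline to year five, first year event-free | 4*h* | 4*h*/5 = 0.8*h* | 5*h*/4*h* = 1.25 | *h*/0.8*h* = 1.25 |
| B. One-year cytology to year five | 4*h* | 4*h*/4 = *h* | 5*h*/4*h* = 1.25 | 1.00 |
| C. One-year cytology plus five years | 5*h* | 5*h*/5 = *h* | 1.00 | 1.00 |

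Under A, NILM risk and rate are each 0.80 of the value obtained when counting starts at the one-year cytology, an understatement of 20%.

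**Common landmark.** If both groups start at 12 months, cancer-free, and run to year five, each has risk 4*h* and rate *h*. Both ratios are 1.00.

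**Dependence on *h*.** The exact ratio (1 − e^(−5h)) / (1 − e^(−4h)) is 1.2498 to 1.2499 for *h* = 0.01%, 0.02% and 0.04% per year, so the unknown rate does not matter when events are rare.

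**Timing of the one-year test.** The plan gives no window. Assuming 9, 12 or 15 months, 5/(5 − t/12) gives 5/4.25 = 1.18, 5/4 = 1.25 and 5/3.75 = 1.33. The NILM rate under A is understated by 15%, 20% and 25%.

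**Data needed.** The landmark comparison to year five needs follow-up to December 2018 + 5 years = December 2023. Window C needs December 2018 + 1 + 5 years = December 2024, or March 2025 if the one-year test can fall at 15 months. The documents do not give the end date of the extract.

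**The case against.** The strongest reply is that the plan never says NILM time starts at baseline. A NILM woman meets the inclusion criteria only at her one-year cytology, so enrollment can naturally mean that date. The Summary also describes these women as going back to routine screening after that test. With five years from there, the artefact is nil at constant hazard. This stands. A reader might infer that the comparison is certainly misaligned, but the documents support only an unstated origin that misaligns it under some readings. Section 5.1.1 concerns low-grade women only. The extra three months in the histology analysis do not prove a convention that was then forgotten for NILM: no reason is given for them, and the 12-month cytology strata in the same analysis get no further extension.

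The direction is cautious for the main question. An understated benchmark makes low-grade women look relatively worse, which argues against reducing their follow-up. The Summary also mentions follow-up of women with persistent NILM results; for them an understated risk would be falsely reassuring.

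The size can also be questioned. With equal event counts, a ratio of 1.25 differs from 1 at the 95% level only with about 2/(ln 1.25/1.96)² = 154 cancers per group. With fewer events the artefact is smaller than sampling error, though it remains a bias that is easy to avoid.

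A reader might also infer that cancers found at referral inflate the low-grade incidence and should be removed. The plan does not support that: they are real risk and belong in the five-year total. Time to diagnosis, examination type and the histology and cytology strata already show part of the early/late split. What is missing is its use in the NILM comparison. The share of the contrast due to these cancers cannot be derived from the documents.

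**Conclusion.** The point holds as a gap in specification with a calculable consequence. Under the plain reading of section 3, five years for the whole cohort, the low-grade/NILM ratio is 1.25 on both measures when the true ratio is 1.00. Counting NILM time from the one-year cytology to year five leaves 1.25 on cumulative incidence and 1.00 on the rate. Five full years from that cytology gives 1.00 on both.

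These figures assume equal constant hazards, rare events and a test at exactly 12 months; they illustrate size and do not predict the result. Whichever NILM clock is used, first-year cancers are selected out of the NILM group and kept in the low-grade group, and the planned comparison does not display this. The primary low-grade incidence is not affected. The gap should be closed because this secondary comparison carries the policy interpretation.

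**What to change.** Amend section 6.2 as follows.

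1. Start NILM person-time at the one-year cytology, define enrollment and state the window for each group. Do not compare cumulative incidences over windows of unequal length.
2. Keep the low-grade five-year total from baseline. Add a comparison from a common 12-month landmark among women cancer-free at that point, followed in both groups to five years from baseline. Label it residual risk after work-up, not a replacement for the total. If one-year tests after 12 months are accepted, set the landmark at the end of the accepted window so that no event-free time re-enters.
3. Show low-grade cancers diagnosed before the landmark as a separate row.
4. Report the risk difference and ratio with 95% CI. Section 6.2 currently names no contrast.

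Five full years from the one-year cytology can be an optional sensitivity analysis if the extract reaches that far. It takes NILM women into year six from baseline, past the next five-yearly invitation (section 1), so next-round screen-detected cancers should be shown separately.

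The cost is SAP wording and one extra table. The landmark comparison needs no follow-up beyond the planned five years, and section 5.1.3 already plans for follow-up cytology and histology. The downside is fewer events and wider intervals after the landmark.

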3. STUDY DESIGN

This retrospective cohort study includes women who participated in the Dutch national cervical cancer screening program between January 2017 and December 2018, with a follow-up period of five years.

4. STUDY POPULATION

4.1 Population (base)

The study population consists of women who participated in the Dutch national cervical cancer screening program between January 2017 and December 2018. Eligible women were HPV-positive at baseline with either low-grade cytological abnormalities (ASC-US, AGC, LSIL) or stable NILM cytology one year after initial screening.

4.2 Inclusion criteria

To be eligible to participate in this study, a participant must meet the following criteria:

- Women participating in the Dutch national cervical cancer screening program between January 2017 and December 2018.
- HPV-positive at baseline screening.
- One of the following cytology results:
 - ASC-US, AGC, or LSIL cytology according to the Bethesda system

or

- NILM cytology at one-year follow-up.

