5.1.2 Secondary study parameters/endpoints

- Time to diagnosis of cervical cancer.
- All-cause mortality.
- Type of examination at which cervical cancer diagnosis was established.
- Histological characteristics of carcinoma (subtype).
- Cervical cancer incidence in women with stable NILM cytology after one year.
- Cervical cancer incidence in women with a history of abnormal cytology or histology.
- Cervical cancer risk stratified by histological diagnosis within three months of baseline abnormal cytology (\leq CIN I vs $>$ CIN I) and, for the \leq CIN I group, further stratified by cytology at 12-month follow-up (no or nondiagnostic cytology, \leq LSIL, $>$ LSIL).

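### The stable-NILM group must have a one-year cytology and the low-grade group need not, so their planned comparison partly reflects who had a one-year test

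*Combined protocol and SAP*

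**What the plan says.** Both groups are HPV-positive at baseline. Under section 4.2 a woman joins the comparator on "NILM cytology at one-year follow-up"; section 4.1 describes the same group as having "stable NILM cytology one year after initial screening". She joins the low-grade group on "ASC-US, AGC, or LSIL cytology according to the Bethesda system", with no later visit required. Section 4.3 states: "There are no exclusion criteria".

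The second secondary objective (section 2) takes low-grade women with histology of CIN 1 or less within three months, "further stratified by cytology at 12-month follow-up (no or nondiagnostic cytology" being the first of three levels. The plan therefore expects low-grade women without a usable 12-month result and keeps them.

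The fourth secondary objective is to estimate incidence in the stable-NILM group and "compare it to the five-year incidence in women with low-grade cytological abnormalities". Section 6.1 computes cumulative incidence as cases "divided by the total number of women included in the cohort". Section 6.2 provides cumulative incidence and incidence rates for the NILM group and for the strata. It gives no comparative method, no restriction by 12-month testing and no caveat about it.

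**The concern.** One side of the comparison contains only women with a diagnostic cytology at one year. The other mixes women with and without one. Women without a 12-month result may differ in their underlying cancer risk, and also in the chance that a cancer is found within the follow-up window. Some of the observed difference between low-grade and stable-NILM women could then come from testing rather than from the index cytology.

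The Summary's rationale uses this comparison to judge whether follow-up can safely be made less intensive, with stable NILM as the reference because those women already return to routine screening. A distortion in either direction would bear on that judgement. Starting both clocks at one year would not be enough by itself, because women without the test would still be present on one side only.

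**Working it through.** **Step 1. Entry rules side by side.**

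| | Stable NILM | Low-grade |
|---|---|---|
| Result that qualifies (4.2) | NILM at the one-year test | Index cytology |
| One-year cytology needed? | Yes, and it must be diagnostic | No |
| Removed if none? (4.3) | Cannot enter | Not removed |
| Counted in the comparison (section 2, 6.1, 6.2) | Women with the test | Women with and without the test |

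The asymmetry follows from the text and needs no assumption.

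**Step 2. Possible size.** The documents state no expected rate, event count, sample size or share without 12-month cytology, so there is no figure to reproduce. As an illustration, take low-grade women alive and cancer-free at 12 months. Let q be the share without a diagnostic 12-month cytology, and R their later observed cancer risk divided by that of women who have one. Both are assumptions.

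Risk in all such women ÷ risk in those with a result = (1 − q) + qR = 1 + q(R − 1).

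| q | R = 0.5 | R = 2 | R = 3 |
|---|---|---|---|
| 5% | 0.975 | 1.05 | 1.10 |
| 10% | 0.95 | 1.10 | 1.20 |
| 20% | 0.90 | 1.20 | 1.40 |
| 30% | 0.85 | 1.30 | 1.60 |

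For example, q = 20% and R = 2 gives 1 + 0.20 × 1 = 1.20. The low-grade to NILM ratio is multiplied by this factor. R is below 1 if cancers are found less often in women without a test, and above 1 if those women are at higher risk.

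**Step 3. Why the calculation must start at 12 months.** Counted from baseline, the group without 12-month cytology also holds women who died, and can hold women diagnosed with cervical cancer, before the test was due. For the latter, the missing cytology is a consequence of the outcome.

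Suppose that a share s = 30% of low-grade cancers arises in year one, all in women without 12-month cytology, and that later risk is the same with or without a test. Take q = 20% at baseline, and treat cancers and deaths as rare.

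- Share of cancers in women without cytology: 0.30 + 0.70 × 0.20 = 0.44.
- Share in women with it: 0.70 × 0.80 = 0.56.
- Apparent relative risk: (0.44 ÷ 0.20) ÷ (0.56 ÷ 0.80) = 2.20 ÷ 0.70 = 3.14.
- Apparent multiplier: 1 + 0.20 × 2.14 = 1.43, which equals 1 ÷ (1 − 0.30).

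A factor of 1.43 appears although testing has no effect at all; it consists entirely of year-one cancers. A contrast restricted to women with a 12-month result, without a landmark condition on the group left out, would credit those cancers to attendance.

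**Step 4. Do the planned strata already settle it?** No. The 12-month split applies only to histology of CIN 1 or less. Its follow-up is five years and three months from enrollment (section 2), not from the 12-month test. Nothing in section 6.2 links it to the NILM comparison.

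**The case against.** The strongest reply is that the comparator is meant to be what it is. It represents women whom current practice returns to routine screening, and they are defined by the one-year NILM result. For low-grade women the policy question arises at the index result, when later attendance is unknown, so all of them form the natural denominator. This stands. It is the reason to keep the whole-group comparison, but it does not remove the need to say what that comparison contains.

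A second reply is that restricting to women with a 12-month result conditions on something that happens after baseline and drops year-one cancers, which matter for safety. Nor does it make the groups alike: stable NILM is selected on a favourable result, while low-grade women with a 12-month result may have HSIL+. This also stands, so the restricted contrast can only be supportive.

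A third reply is that the strata already display women without 12-month cytology. That is partly true, within the limits in step 4 of the working.

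A reader might infer that the low-grade group is shown to include women who never came back. The documents do not show that. The stratum concerns 12-month cytology within a group that already has histology within three months, and a nondiagnostic sample means that the woman attended. Women with no follow-up at all are not excluded, but the plan does not say that there are any.

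**Conclusion.** The asymmetry is real and is unaddressed in section 6. It affects the fourth secondary objective only; the primary endpoint is a single-group incidence and is untouched. Neither size nor direction can be derived from the documents. The range of 0.85 to 1.60 rests wholly on assumed q from 5% to 30% and R from 0.5 to 3, and shows only that the distortion could go either way.

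A reader might go further and conclude that the comparator is wrongly chosen, or that the comparison is biased by a known amount. The documents support neither: the benchmark has a stated purpose, and no share or risk is given. This is a worthwhile, inexpensive improvement to a secondary analysis, not a flaw that invalidates the study.

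**What to change.** Keep the planned whole-group comparison as the policy benchmark, with year-one low-grade cancers still reported in it. In section 6.2 add a supportive 12-month landmark comparison:

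- Take low-grade women alive and without cervical cancer at 12 months, across all histology results.
- From that point, report cumulative incidence and incidence rates separately for women with a diagnostic 12-month cytology (overall, and by result: ≤ LSIL, HSIL+) and for women without one.
- Set these beside stable NILM counted from its one-year test. Use the same length of follow-up on both sides; with five years from baseline, 5 − 1 = 4 years remain for low-grade women.
- State the time window within which a sample counts as the 12-month cytology.

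Add two sentences of interpretation. The first says that the whole-group contrast also reflects having had a one-year test. The second says that the landmark contrast describes women with a 12-month result, omits year-one cancers, has fewer events, and does not make the groups exchangeable because stable NILM is also selected on a favourable result.

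Follow-up cytology is already a study variable (sections 5.1.3 and 6.3), and time to diagnosis and mortality are already endpoints, so the variables are planned. The 12-month classification must be extended beyond the CIN 1 or less group, which is a little extra work. The cost is one more table, with lower precision and a narrower population in that table.

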4.3 Exclusion criteria

There are no exclusion criteria.

5. METHODS

5.1 Study parameters/endpoints

5.1.1 Main study parameter/endpoint

- Incidence of histologically confirmed cervical cancer within the five-year screening interval in HPV-positive women with low-grade cytological abnormalities.

5.1.2 Secondary study parameters/endpoints

- Time to diagnosis of cervical cancer.
- All-cause mortality.
- Type of examination at which cervical cancer diagnosis was established.
- Histological characteristics of carcinoma (subtype).
- Cervical cancer incidence in women with stable NILM cytology after one year.
- Cervical cancer incidence in women with a history of abnormal cytology or histology.
- Cervical cancer risk stratified by histological diagnosis within three months of baseline abnormal cytology (\leq CIN I vs $>$ CIN I) and, for the \leq CIN I group, further stratified by cytology at 12-month follow-up (no or nondiagnostic cytology, \leq LSIL, $>$ LSIL).

5.1.3 Other study parameters

- Baseline characteristics such as age at inclusion.
- Cytology according to the Bethesda system and histology results at baseline and follow-up.
- HPV test results at baseline and follow-up.
- Relevant medical history, including prior abnormal cytology or histology.

6. STATISTICAL ANALYSIS

6.1 Primary study parameter(s)

The primary study parameter is the incidence of histologically confirmed cervical cancer within the five-year follow-up period. The cumulative incidence will be calculated as the number of new cases diagnosed divided by the total number of women included in the cohort. The incidence rate will also be calculated as the number of cervical cancer cases divided by the total follow-up time in person-years and expressed per 1,000 person-years.

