6.2 Secondary study parameter(s)

Secondary study parameters include:

- Time-to-diagnosis of cervical cancer, which will be displayed in a line diagram with time on the y-axis and number of cases on the x-axis.
- All-cause mortality, type of examination at which the diagnosis was established, and histological subtype of cervical cancer, which will be summarized as frequencies and percentages for each relevant group.
- Cervical cancer incidence in women with stable NILM cytology after one-year follow-up, cervical cancer incidence in women with a history of abnormal cytology or histology, and risk stratification by histology within three months of baseline cytology and follow-up cytology at 12 months. For these parameters, cumulative incidence and incidence rates will be calculated.

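### No confidence interval is planned for any incidence, and time to diagnosis is shown as case counts without a denominator, although the study must judge a small risk and compare two groups

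*Combined protocol and SAP*

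**What the plan says.** Section 6.1 defines two measures for the primary parameter. The first is a proportion: "The cumulative incidence will be calculated as the number of new cases diagnosed divided by the total number of women included in the cohort". The second follows directly: "The incidence rate will also be calculated as the number of cervical cancer cases divided by the total follow-up time in person-years", expressed per 1,000 person-years.

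Section 6.2 covers the stable NILM group, the women with prior abnormal cytology or histology, and the strata by early histology and 12-month cytology: "For these parameters, cumulative incidence and incidence rates will be calculated". Time to diagnosis is to be "displayed in a line diagram with time on the y-axis and number of cases on the x-axis". All-cause mortality is reported as frequencies and percentages.

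Section 2 sets a comparison: evaluate incidence in the stable NILM group and "compare it to the five-year incidence in women with low-grade cytological abnormalities". Section 3 describes the cohort "with a follow-up period of five years"; section 2 gives the stratified analysis five years and three months.

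Sections 6.1 to 6.3 are the whole statistical plan. They name no confidence interval, standard error, time-to-event estimator or measure of contrast between groups. They do not say when person-time starts and stops.

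**The concern.** The Summary and section 1 give the purpose as judging whether follow-up intensity can safely be reduced, and section 1 describes the long-term cancer risk as relatively low. A claim of safety rests on the upper end of the plausible risk. If the plan is followed as written, each result is a bare proportion and a bare rate, and a reader cannot tell what risk has been excluded. The problem is sharpest in the strata: the group with CIN 1 or less is split three ways by 12-month cytology, and a stratum with few or no cancers could be read as reassuring when the data are merely sparse.

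The NILM versus low-grade comparison has the same gap. Two point estimates side by side do not show whether a difference, or a similarity, is more than chance.

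The time display adds little. A line of case counts has no denominator, so it does not show risk over time and cannot be read across groups of different size.

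**Working it through.** **Is there a figure to reproduce?** No. The documents state no sample size, expected number of cancers, confidence level or loss rate. All counts below are assumptions chosen to show scale.

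**1. Precision of the proportion.** With c cancers in N women, the exact (Clopper-Pearson) 95% limits are the 0.025 quantile of Beta(c, N − c + 1) and the 0.975 quantile of Beta(c + 1, N − c). For c = 0 the lower limit is 0 and the upper limit is 1 − 0.025^(1/N).

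| Assumed cancers / women | Estimate per 1,000 | Exact 95% limits per 1,000 |
|---|---|---|
| 10 / 10,000 | 1.00 | 0.48 to 1.84 |
| 3 / 2,000 | 1.50 | 0.31 to 4.38 |
| 0 / 500 | 0 | upper limit 7.4 (0.74%) |
| 0 / 1,000 | 0 | upper limit 3.7 (0.37%) |

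For a rare event the relative width depends almost only on the number of cancers: about 0.32 to 2.33 times the estimate with 5 cases, 0.61 to 1.54 with 20, and 0.74 to 1.32 with 50.

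**2. Precision of the rate.** With person-years T, the exact Poisson limits are χ²(0.025; 2c)/(2T) and χ²(0.975; 2c + 2)/(2T). If all 10,000 women contribute five years, T = 50,000. Ten cancers then give 10/50,000 = 0.20 per 1,000 person-years, with limits 0.10 to 0.37. The rate needs an interval as much as the proportion does.

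**3. When is cases/N biased?** Treat death as a competing event. With no other censoring before 60 months, the number at risk just before each cancer, divided by N, is exactly the proportion still event-free. Each cancer therefore adds 1/N to the Aalen-Johansen estimate, and the total at 60 months is cases/N. The same holds for hysterectomy if it is treated as a competing event. Neither makes the crude proportion too low as an estimate of that quantity.

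True loss to observation, such as emigration, does. With constant hazards h for cancer and l for independent loss, the expected crude proportion is h/(h + l) × [1 − exp(−5(h + l))]. For an assumed true five-year risk of 0.5%:

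| Assumed loss by five years | Expected cases/N | Relative shortfall |
|---|---|---|
| 0% | 0.500% | 0 |
| 2% | 0.495% | 1% |
| 5% | 0.487% | 2.5% |
| 10% | 0.475% | 5% |
| 20% | 0.448% | 10% |

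Under the same model the person-year rate stays at 1.0025 per 1,000 in every row, so the planned rate is not distorted by such loss.

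**4. Are windows cut short by the calendar?** Screening participation ended in December 2018. Five years later is December 2023, and five years and three months later is March 2024. The protocol is dated November 2025. The extract date is not given, but nothing indicates truncated follow-up.

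**The case against.** The strongest reply is that the plan already takes account of time. The sentence after the definition of the proportion divides cases by "total follow-up time in person-years", and section 6.2 repeats this for the secondary groups. In a cohort with essentially complete five-year observation, cases/N is also the correct cumulative incidence. Both points stand. A reader might infer that the main results ignore follow-up time; the text does not support that. What ignores it is the proportion and the case-count diagram.

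A reader might also infer that women who die or have a hysterectomy bias the primary result by staying in the denominator. An analysis with those as competing events keeps them there too and gives the same answer when there is no other censoring.

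The reversed axes are a presentation matter and change no estimate. Section 6.2 also does not say that the diagram is meant to compare groups.

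None of this answers the missing intervals. It also leaves the person-time for the planned rate without a stated start, stop or censoring rule.

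**Conclusion.** The point holds, mainly on precision. As written, the plan gives point estimates of a small risk, and a comparison of two such estimates, with no statement of uncertainty. On assumed counts the omitted information is large: with 10 cancers the upper limit is 1.84 times the estimate, with 3 it is about 2.9 times (4.38/1.5), and 0 in 500 does not exclude 0.74%. The uninformative time display and undefined person-time are real but smaller.

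Bias in cases/N is a possibility of unknown size. It requires true loss to observation, for which the documents give no figure. At an assumed 2% to 5% loss it is 1% to 2.5% relative, well inside sampling error at the counts illustrated. A reader might conclude that the primary estimate is materially too low; the documents do not show this.

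Groups formed at three or twelve months also raise a question of delayed entry. Moving to a time-to-event estimator from enrolment would not by itself settle that, so it is not claimed here as part of the remedy.

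**What to change.** In sections 6.1 and 6.2:

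- Give an exact 95% CI with every cumulative incidence (Clopper-Pearson for the proportion, or the interval belonging to the time-to-event estimator) and an exact Poisson 95% CI with every rate.
- Report the NILM versus low-grade contrast as a difference or ratio with a 95% CI.
- State that person-time runs from enrolment to the first of cancer diagnosis, death where dated, last known observation, or end of the stated window. Define last known observation: the absence of a later pathology record should not on its own count as loss.
- Replace the case-count diagram with cumulative incidence curves by group, time on the x-axis and numbers at risk beneath. Use Aalen-Johansen with death as a competing event where deaths are dated, otherwise 1 minus Kaplan-Meier. Report the 60-month estimate beside the crude proportion. With no dated loss the two will coincide, which is itself worth showing.
- Treat hysterectomy as a competing event only if its date is in the extract. Sections 5.1.2 and 5.1.3 do not list it, so its availability should not be assumed.

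The cost is SAP wording and a little more analysis, largely on dates already needed for the person-year rate. The sponsor should confirm that the software named in section 6.3 provides these estimators. The one real downside is that low-count strata will look less reassuring, which is an accurate reflection of the data.
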